#### **6.3 Crossover Procedures**

There will be three crossover conditions during this study. Each participant will be given five of each study condom set and will have up to four weeks to use all five condoms.

If five coital log events are recorded by the end of the two-week follow-up visit for any crossover condition, participants will be crossed over to the next crossover condition or determined to have completed the study (after completing five coital log events for the third study condom set). If five coital log events are not recorded by the end of the two-week follow-up, participants will be given another two weeks to use the study condoms in that

[figure not shown]
crossover condition. At the four-week follow-up for the first two crossover conditions, participants will be automatically crossed over to the next crossover condition. Participants will be automatically completed in the study after four weeks on the third crossover condition. The crossover procedures and possible crossover condition combinations are shown in Figures 1 and 2 and Table 1.

#### 7. STUDY PROCEDURES

#### 7.0 Visit Structure

Visual depictions of the baseline and follow-up visit structures are provided below.

Figure 3. Baseline visit structure

eCRF Completion Including count of condoms returned and coital log review Behavioral Survey Adverse Event Screening Asymptomatic Acute HIV Symptoms STI Symptoms Blood draw for viral load testing Undetectable Detectable Referral If all 5 condoms of If all crossover If only first conditions crossover condition Return to visit of completed, or have been used, or complete study crossover Referral this is the second second visit on condition and visit visit of this third crossover <5 used condition , crossover condition Continue on STUDY STOPPED STUDY STOPPED **END OF STUDY** Crossover same condom

Figure 4. Follow-up visit structure

#### 7.1 Visit Procedures

### 7.1.1 Scheduling

Using contact information gathered from primary or secondary recruitment methods, study staff will contact potential participants via phone or email. During the screening call, study staff will assess additional eligibility criteria. Eligible and interested participants will be scheduled for an enrollment (baseline) visit. See Figure 3 for a summary chart of the baseline visit.

#### 7.1.2 Enrollment/Baseline Visit

# 7.1.2.1 Consent for Study Participation

Upon arrival at the baseline visit, participants will be provided with the ICF for study participation. Each participant will be given a chance to review the consent document with and have any questions answered by study staff. Consenting participants and the witnessing study staff will sign the form. Participants will be given a copy of the consent for their own records.

# 7.1.2.2 Eligibility Assessment

- All consenting participants will be screened for eligibility.
- Study staff will complete an electronic Case Report Form (eCRF) to assess eligibility of participants.
- As part of the eligibility assessment, participants will be screened with an eCRF for symptoms of STIs and acute HIV infection (uploaded to eIRB).
  - If the participant self-reports symptoms of any STI, they will be referred to AID Atlanta for testing and treatment as needed. Participants symptomatic for STIs will receive their incentive for the visit and will be ineligible to continue in the prospective study.
  - If the participant has had unprotected anal sex with a man OR has injected a substance not prescribed to him in the past 30 days AND self-reports symptoms of acute HIV infection, blood will be drawn for HIV viral load. Participants being tested for acute HIV infection will continue with their baseline visit, but will not receive study condoms until their results are returned.
    - Once study staff receive their laboratory results, if the
      participant has no detectable viral load, the participant will be
      allowed to continue in the study: they will be randomized,
      shipped study condoms, and scheduled for their next follow-up
      visit.
    - If the participant has a viral load that indicates acute HIV infection, they will be actively linked to HIV care. Results will be returned by study staff experienced in HIV care linkage (scripts uploaded to eIRB). The participant will be study

19

- stopped and will be ineligible to continue in the prospective study.
- Participants will be asked if they currently have a partner who is HIV
  positive. If a current partner is HIV-positive, the participant will be
  study stopped and will receive information on PrEP.

# 7.1.2.3 HIV Testing

- Eligible participants will receive HIV counseling, rapid testing, and results.
   Ineligible participants will be encouraged to receive HIV counseling and testing, but these services will not be required.
  - Participants will receive pre- and post-test counseling per CDC guidelines.
  - HIV rapid testing will be conducted using the INSTI HIV-1 antibody test (described in section 11.0).
    - O Participants with preliminary positive results will be scheduled to receive confirmatory testing at a private location of Emory's choosing. All preliminary positive results will be confirmed with a 4th generation immunoassay with reflex by a study laboratory per CDC guidelines. Participants with preliminary positive rapid HIV test will receive their incentive and their study visit will end at this time.
    - The results of the confirmatory testing will be returned by study staff experienced in HIV care linkage (scripts uploaded to eIRB). Participants with confirmed HIV infection will be ineligible to continue in the prospective study.
    - Participants with two invalid INSTI tests or who are unable to provide enough blood for the INSTI test will be scheduled to receive confirmatory testing and will be paused from study participation until results are delivered.
    - Participants who are confirmed to be negative for HIV infection will be contacted to return to complete baseline visit procedures. Participants can be given a copy of their HIV rapid test result upon request (uploaded to eIRB).

### 7.1.2.4 Baseline Questionnaire

- Participants will complete a self-administered behavioral survey (uploaded to eIRB) on an electronic tablet or study computer including questions in the domains of:
  - Sexual history
  - Condom history
  - Sexual dysfunction
  - Condom slippage and breakage
  - Lubricant use
  - Therapeutic methods

- Condom fit and feel
- Condom perceptions
- Self-efficacy around condom use
- HIV and STI history
- Partner history
- Pleasure

# 7.1.2.5 Participant Training

Study staff will train all eligible participants regarding correct condom use and completion of coital logs. Participant training materials are uploaded to eIRB.

- Study staff will train participants in correct condom use based on a training module that comes from a CDC-determined Effective Behavioral Intervention (DEBI).
  - The eight steps for condom success from the intervention include: putting the condom on before sex, opening the package without damaging the condom, finding the top of the condom, rolling it to the base of the penis, (as needed) adding water-based lubricant to the outside of the condom, wearing condom throughout entirety of sex act including ejaculation, holding the rim of the condom upon withdrawal, and avoiding spilling onto the genitals, mouth or rectum.
  - Study staff will instruct participants to use each condom for one sex act only. If they have multiple sex acts in a session, they should take the condom off between acts and use a second condom.
  - Study staff will instruct participants to only use condom-compatible lubricant provided by the study and to only apply lubricant to the exterior of the condom.
    - MSM will be instructed to use lubricant with all anal sex acts,
       MSW will be instructed to use lubricant as needed
    - Coital log entries indicating incorrect use of lubricant will be excluded from clinical failure analyses (Aims 3 and 4). This includes use of non-study lubricant, use of lubricant inside the condom, and absence of lubricant use for anal sex.
- Participants will also receive training on accessing and completing the home electronic coital log (uploaded to eIRB).
  - For participants without access to the internet and a functioning web browser at home, we will provide smartphones for use during the study.
  - Study staff will go through each question in the log with participants to clarify instructions and answer any questions.
  - Study staff will discuss when participants should complete the log (as soon as possible following intercourse) and how to access the log.

- Participants will be provided with an opportunity to personalize their username and their unique password used for both their login and electronic signature. This will also include information on how to come up with a memorable password and how to reset their username and password if either is forgotten.
- Participants will be asked what time of day they prefer for their daily coital log reminders, and this information will be entered into the scheduling system.
- Study staff will go over the visit schedule with participants.
- Participants will be instructed to return unused study condoms and any condoms that break (to be returned in study-provided biohazard bags) at their follow-up visit. The return and subsequent analysis of broken condoms will be conducted according to instructions detailed in Annex H of International Organization for Standardization (ISO) Guidance Document, ISO TC 157 N 770.
  - O Participants who did not determine their fitted condom size at home will receive information regarding determination of their fitted condom size. This information (video and text) will be identical to that which was received by participants who conducted the procedure prior to their visit. Participants will be asked to determine their fitted condom size at home within 2-5 days of the baseline visit.
  - All participants will enter their fitted condom size into a secure electronic form.

### 7.1.2.6 Distribution of Study Materials

- Study condoms will be provided to participants in batches of five. Each time a participant enters into a crossover condom condition, they will be given the batch of those five condoms, other batches will not be provided until the appropriate crossover time.
  - If we are out of stock of a certain size, participants will be given the next size up length or width.
- Participants will be provided study lubricant, printed study materials such as instructions for proper condom use, and a biohazard bag to return any broken condoms.

### 7.1.2.7 Enrollment and Randomization

- Eligible participants who have completed initial study procedures will be enrolled in the study.
- Participants will be randomized to a study arm, based on methodology specified in section 6.1, once they complete their fitted condom sizing.
  - Participants who choose to complete their fitted condom sizing at home after their baseline visit will be shipped their initial batch of condoms.

# 7.1.3 Follow-up Visits (Week 2, 4, 6, and if applicable, weeks 8, 10, and 12)

At the end of the participant's baseline visit, enrolled participants will be scheduled for follow-up visits at weeks two, four, and six. If the participant is unable to schedule all three visits at this time, or as conflicts arise, visits can be rescheduled as needed.

### 7.1.3.1 Follow-up Preparation

Prior to each visit, study staff will review electronic reports of the following for each scheduled participant:

- The number of condoms were recorded as used in the coital log in the last period
- The study visit number
- The cross-over schedule

# 7.1.3.2 eCRF Completion and Coital Log Review

- During each follow-up visit, study staff will perform a manual count of returned condoms and record this on an eCRF. The number of returned unused condoms will be compared to the number of study condom uses reported in the coital logs, and the number of returned broken condoms will be compared with the number of reported condom breakages.
  - If there are any discrepancies in the staff count and coital logs, study staff will query the participant about the discrepancy and work with the participant to resolve any discrepancies.
  - Discrepancies and how condoms were used that were not reported on coital logs (e.g. lost, MSW using condoms for anal sex) will be reported on an eCRF. If there are previously unreported events, participants will be given a chance to self-complete coital logs for up to two recent condom uses.
  - Study staff will replace any condoms that are lost on non-crossover visits.
- Study staff will review coital log entries with the participant during each visit. Study staff will confirm experiences in the coital log, such as confirming names and information of new partners encountered during the study.

#### 7.1.3.3 Visit Behavioral Survey

- Participants will complete a self-administered behavioral survey (uploaded to eIRB) in the domains of:
  - Condom fit of the last study condom used

23

- Perceived crossover condition
- New sexual partners
- Prior to beginning the third crossover condition, participants will be asked their condom preference between the first two condom types.

### 7.1.3.4 Visit Adverse Event Screening

- Study staff will screen participants for symptoms of a STI or acute HIV infection using procedures from the baseline visit.
  - If the participant self-reports symptoms of any STI at follow-up, they will be referred to AID Atlanta for testing and treatment as needed. Participants symptomatic for STIs will receive their incentive for the visit and be study stopped. This will be recorded as an adverse event. See section 8.1.2 for more detail regarding adverse event reporting.
  - If the participant has had unprotected anal sex with a man OR has injected a substance not prescribed to him in the past 30 days AND self-reports symptoms of acute HIV infection, blood will be drawn for HIV viral load. Participants with acute HIV infection symptoms will receive their incentive and their study visit will end at this time.
    - Once study staff receive their laboratory results, if the participant has no detectable viral load, the participant will be allowed to return to complete their study visit. We will ship participants their next batch of condoms and schedule them for their next follow-up visit two weeks later.
    - o If the participant has a viral load that indicates acute HIV infection, they will be actively linked to HIV care. Results will be returned by study staff experienced in HIV care linkage (scripts uploaded to eIRB). The participant will be study stopped and study staff will record this as an adverse event.
- Study staff will ask participants if they have experienced any discomfort or issues related to the study condoms. If they indicate any, participants may be asked to have a picture taken of the reaction for the study clinician's assessment. Depending on the severity of issues, as determined by the clinical judgment of the study physician, they may be study stopped.
- For MSW participants, study staff will ask whether their current partner is pregnant.
  - If that participant indicates that their partner is pregnant and the expected date of conception is during the study or unknown, their partner will be referred to the Grady Family Planning Wellness Clinic and study staff will record this as an adverse event.

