#### 4.4 Participant Withdrawal

Participants may voluntarily withdraw from the study for any reason at any time. The study investigators also may withdraw participants from the study in order to protect participant or staff safety. Study staff will record the reasons for all withdrawals or holds from the study on a Study Stop Form in the participants' study records. Study stoppage may occur for the following reasons:

- Participants who self-report symptoms of STIs (described in more detail in section 7.1.2.2) will be referred to AID Atlanta for testing, but will be study stopped and will not attend follow-up visits.
- Participants who: (a) report that their current partner(s) is HIV-positive; (b) that they have had sex with someone in the past 30 days who is HIV-positive and plan to have sex with that partner again; or (c) add a new partner in the coital log who is HIV-positive

- during the study, will be study stopped and given information on pre-exposure prophylaxis (PrEP).
- Participants also may be withdrawn if the study is terminated prior to its planned end date.

Participants may be temporarily held from the study for the following reasons:

- Participants who have had unprotected anal sex with a man OR injected a substance not prescribed to them in the past 30 days AND self-report symptoms of acute HIV, such as fever over 100°F, at baseline or follow-up visits will be paused until a viral load test is performed. Participants will be study stopped if they have a detectable viral load; participants can resume study visits if their viral load is undetectable.
- Participants with a preliminary positive rapid HIV test at baseline will be paused until results of a confirmatory test are received. Participants will be study stopped if they are confirmed to be HIV positive; confirmed HIV negative participants will be asked to return to complete their baseline visit.
- Participants experiencing discomfort or issues related to the study condoms or lubricant will be paused until the study physician can assess the severity of issues. Participants will be study stopped if the physician determines it is in the participant's best interest to discontinue participation in the study.

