Based on previous trials, we expect possible adverse events (AE) to include symptomatic and asymptomatic STIs (particularly in area not covered by condom), acute HIV infection, discomfort or other issues related to the study condoms or lubricant, and pregnancy (for current partner of MSW) (described in Section 8.1.1).

If any adverse event occurs at a rate of 1.5 times greater than expected, the principal investigator will consider unblinding the study at the investigator level, in consultation with the study physician. Assuming that we will follow people on average for 10 weeks, we expect chlamydia and gonorrhea among MSW to occur among less than 0.5% of participants during the study period, based on 2013 surveillance data for men in Georgia. Based on estimates from a previous study in Atlanta we expect urethral chlamydia and gonorrhea among MSM to occur among less than 1% of participants and rectal chlamydia and gonorrhea among MSM to occur among less than 4% of participants during the study period.

Given that there is a 50-90% rate of acute symptoms among incident HIV infections and an 11% incident rate of HIV observed among young black MSM in Atlanta, we expect over the 6-10 week study period acute HIV infection among 1.3% of MSM participants. Because there are limited data available regarding incidence HIV rates among MSW in Atlanta, we estimate acute HIV infections to be one-fifth of that for MSM, or 0.25% of MSW participants.

Discomfort or other issues related to the study condoms or lubricant are expected to occur at a rate of 20% ([name], email communication, August 11, 2015). Pregnancy for current partners of MSW is expected to occur among less than 4% of partners during the study period. However, we expect 52% of MSW and their current partners will not be using condoms as the main form of birth control.

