#### 7.2.5 Reactions/Side Effects to Condoms

Study staff will consult with an independent physician regarding the severity of any reactions or side effects to the study condoms. As appropriate, participants will be referred to AID Atlanta and study stopped.

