## 8.1 Adverse Event Definitions and Reporting Requirements

#### **8.1.1** Adverse Events Definitions

### 8.1.1.1 Adverse Events

An AE is defined as any unfavorable or unintended sign (including laboratory findings), symptom or disease that occurs to a subject while enrolled in a clinical trial that could be associated with the use of the study intervention. Medical conditions that exist at study enrollment are not considered an AE unless condition worsens after use of the study intervention.

In this study, the study intervention includes provision of condoms, lubricant, and HIV testing and counseling. Possible adverse events for all participants include symptomatic STI infection, acute HIV infection, discomfort or other issues related to the study condoms, and pregnancy (for current partner of MSW).

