## 8.1.2 Adverse Events Reporting

Study participants will receive instructions to report any untoward medical occurrences that could be associated with the study intervention to study staff, except for possible life-threatening events, where they will seek immediate emergency care. If the participant receives care from a provider outside of the study for an AE, with permission of the participant, records from that visit related to the untoward medical occurrence will be received by study staff as determined by the study physician. Study staff will document all AEs observed in or reported by participants in the AE eCRF, regardless of severity of presumed relationship to the study interventions or product. Participants who experience reactions or side effects to the study condoms or lubricant may be asked to have a picture taken of the reaction. This picture will be shared only with the study clinician for AE determination and will not be entered as study data. The principal investigator will have final determination in severity, relatedness (to study intervention), and whether the AE is considered to be anticipated or unanticipated.

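### The follow-up adverse event question names study condoms only, while the category the protocol pauses men for and benchmarks at 20% is condoms or lubricant

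*Protocol*

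**What the plan says.** The protocol describes one category of product reaction in two ways.

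**Condoms only**
- 7.1.3.4, the question put at follow-up visits: "Study staff will ask participants if they have experienced any discomfort or issues related to the study condoms".
- 7.2.5, where staff consult a physician: "regarding the severity of any reactions or side effects to the study condoms".
- 8.1.1.1, the list of possible adverse events: "discomfort or other issues related to the study condoms, and pregnancy (for current partner of MSW".

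**Condoms or lubricant**
- 4.4, temporary holds: "Participants experiencing discomfort or issues related to the study condoms or lubricant will be paused until the study physician can assess the severity".
- 6.2, expected adverse events, with a pointer to the adverse event section: "discomfort or other issues related to the study condoms or lubricant, and pregnancy (for current partner of MSW) (described in Section 8.1.1".
- 6.2, expected rate: "Discomfort or other issues related to the study condoms or lubricant are expected to occur at a rate of 20"%. In the same section, an event running at 1.5 times its expected rate leads the principal investigator to consider unblinding at investigator level.
- 8.1.2, photographs: "Participants who experience reactions or side effects to the study condoms or lubricant may be asked to have a picture taken of the reaction".
- 10.2 lists reactions to condoms and lubricant together as a risk.

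The definition of the intervention in 8.1.1.1 also covers lubricant: "the study intervention includes provision of condoms, lubricant, and HIV testing and counseling".

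The SAP deals with Aims 1 to 4 and their measures. It does not describe how product reactions are collected or summarized.

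**The concern.** A rate can be compared with a benchmark only if the numerator is collected on the definition the benchmark uses. Here the 20% figure and the pause rule refer to condoms or lubricant, but the question that would produce the numerator mentions condoms.

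A participant need not hear 'study condoms' as including the study lubricant. Section 5.3 supplies the lubricant separately, as packets of a water-based product. The Introduction describes a different, silicone lubricant already on the condom. Section 4.1.2 excludes men with an allergy to water-based lubricant as a criterion in its own right. A man who blames the packet for his irritation could truthfully answer no.

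Two things are at stake. A man who should be paused for physician assessment under 4.4 may not be identified at the visit. The observed reaction rate may also sit below the rate in the category that 6.2 monitors.

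**Working it through.** The plan has no figure to reproduce on this point, so the check is mainly a comparison of text.

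**Step 1. Is the mismatch internal to the protocol?** Yes. Section 6.2 names condoms or lubricant and refers the reader to 8.1.1 for the description, but the list there leaves lubricant out. Within 8.1.1.1, one sentence puts lubricant in the intervention and the next gives examples that omit it.

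**Step 2. Does another solicited item fill the gap?** None is visible. The visit survey domains in 7.1.3.3 are the fit of the last condom used, perceived condition, new partners and, before the third condition, preference. The coital log topics in 7.1.6 and 7.3.3 include whether lubricant was used, but not a reaction to it. Section 7.3.1 says that the follow-up case report forms collect adverse events, without giving their wording.

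**Step 3. Is there an unsolicited route?** Yes. Section 8.1.2 tells men to report untoward occurrences that might be linked to the intervention, and staff document all adverse events observed or reported. With lubricant in the intervention, a volunteered lubricant reaction is recorded.

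**Step 4. What could this do to the benchmark comparison?** Inputs: expected rate 20% and factor 1.5 (6.2); planned enrollment 504 (9.3). The 20% is taken as a rate per participant, which 6.2 does not state.

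- Expected count: 0.20 × 504 = 100.8, about 101 men.
- Review mark: 1.5 × 20% = 30%; 0.30 × 504 = 151.2, about 151 men.

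Let s be the share of events in the category that are due to lubricant alone and go unrecorded. Then observed rate = true rate × (1 − s), and the true rate at which the observed rate reaches 30% is 30% / (1 − s).

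| s (assumed) | True rate when 30% is observed |
|---|---|
| 0% | 30% |
| 10% | 0.30 / 0.90 = 33% |
| 25% | 0.30 / 0.75 = 40% |
| 33% | 0.30 / 0.67 = 45% |

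The documents give no value for s. The table shows direction and sensitivity only. It does not estimate missed reactions.

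**The case against.** The best defense is that this is loose drafting that other text makes good. The adverse event definition in 8.1.1.1 covers anything that could be linked to the intervention, lubricant included, and the list that follows gives examples. It differs from the list in 6.2 in another respect too: 6.2 includes asymptomatic infections and 8.1.1.1 does not. That points to informal writing, not a deliberate narrowing. Section 8.1.2 captures volunteered reports, and 4.4 already brings in the study physician for lubricant problems, so the omission in 7.2.5 has little practical effect. Section 7.1.3.4 reads as a summary of procedure, not a script, and the form may name lubricant. Because lubricant goes on the outside of the condom (7.1.2.5), many men with discomfort would answer yes anyway.

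Most of this stands. It rules out a stronger reading that a reader might infer, namely that lubricant reactions fall outside adverse event reporting. The definition and 8.1.2 say otherwise.

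It does not remove the remaining point. Spontaneous reporting does not replace asking, and the one product-reaction question shown is narrower than the event that triggers a pause. The unseen form could settle what staff ask, but 7.2.5 and the list in 8.1.1.1 would still disagree with 4.4, 6.2 and 8.1.2.

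**Conclusion.** The point holds as a minor gap in safety ascertainment. As written, the follow-up question solicits condom-related problems only, while the pause rule and the 20% benchmark cover condoms or lubricant. The observed rate may therefore be too low for that comparison, by an amount the documents do not allow one to estimate.

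This rests on 7.1.3.4 reflecting what staff ask, and on some men with lubricant reactions neither volunteering them nor attributing them to the condom. If the form already names lubricant, only the inconsistency in the protocol text remains.

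Three further inferences are not supported:
- **That the 1.5-times mark would be missed.** No lubricant-specific rate is given, and the basis of the 20% is not described beyond a personal communication. Reaching the mark would in any case prompt consideration of unblinding, not an automatic step.
- **That partner reactions are under-recorded adverse events.** The definition in 8.1.1.1 concerns the enrolled subject, and partner reactions are not among the listed events.
- **That the condom comparisons are biased.** Section 5.3 describes the same lubricant supply per condom whatever the condition. Aims 1 to 4 rest on pleasure, preference and clinical failure. No efficacy or label conclusion changes.

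**What to change.** 1. In 7.1.3.4, and in the form if it lacks the words, extend the question to cover the study condoms **or lubricant**.
2. Add the same two words to the consult sentence in 7.2.5 and to the example list in 8.1.1.1, so that both agree with 4.4, 6.2 and 8.1.2.
3. If follow-up is already complete, state the wording that was asked beside the reported reaction rate, so that readers know whether lubricant reactions were solicited.

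The cost is a minor wording amendment submitted to the IRB. It needs no added visit or procedure.
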